## 4.4 END OF STUDY DEFINITION

To be considered a "completer" of the study, a participant must:

1. Be placed into the study treatment.
2. Complete the 6-month intervention.
3. Complete both outcome assessments (baseline and 6-months).
4. Complete the follow-up assessments (3-months post-intervention).
5. Have available outcome data on UTI occurrences during the study period as well as during the six months prior to study participation.
6. Complete a safety review with a study team member within 30 days after administering last study drug dose to assess any adverse health/safety events, as required by the FDA.

The end of the study data collection will be when the last participant accrued completes their final assessment.

## 5 STUDY POPULATION

Participants who had previously been enrolled in this clinical trial and did not complete the intervention due to the study having been put on hold for an extended period will be allowed to re-enroll if they still meet the criteria for participation listed below.

### 5.1 INCLUSION CRITERIA

The electronic medical record (EMR) will be pre-screened for all inclusion criteria prior to the baseline interview and initial lab work. Criteria will be confirmed by patient or caregiver report at the screening assessment.

- Provision of signed and dated informed consent form.
- Male or female 18 years or older at time of enrollment.
- History of traumatic SCI or non-traumatic spinal cord disease (SCD), with sustained neurological dysfunction. Traumatic and non-traumatic SCI/D are defined according to the International SCI Standards and Datasets.
- At least 6-months post-initial hospital discharge following SCI/D onset.
- Neurogenic bladder.
- Ability to self-perform daily instillation or with help of others and willingness to adhere to the study regimen.
- Negative pregnancy test (for females of childbearing age) and expresses willing and ability to use appropriate contraception while enrolled in the study.
- History of at least 2 UTIs documented in the EMR during the previous six months (prior to screening).
- Have a designated physician or health care provider for routine urological care who is a member of Michigan Medicine.
- Use of clean intermittent catheterization (CIC) or catheterization through a stoma (i.e. Mitrofanoff) as their primary method of bladder management
- Agreement to adhere to Lifestyle Considerations (see below) throughout participation in the study and to complete the daily dosing log as instructed by the study coordinator.

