### 1.3 SCHEDULE OF ACTIVITIES (SOA)

Procedures	Screening	Visit 1 (Baseline) 	Visit 2	Visit 3 (Follow-Up Interview)	Optional Post-Intervention Survey
	Day -30 to 0	D0	Day 180±30	Day 90 - 30 / + 90 post-intervention	Day 90 - 30/+365 post-intervention
Medical Record Review	X	X	X	X	
Informed consent		X			
Demographics	X				
Clinical History	X	X	X	X	
Current Medications	X	X	X	X	
Urine Analysis (UA; plus culture if needed) 	X		X		
Pregnancy test	X				
Complete Blood Count		X	X		
Comprehensive Metabolic Panel		X	X		
Self-report measures of QOL 		X	X		
Safety Review 			X		
Every 30 days +/- 2 business days: ship study product		↔			
Schedule bi-weekly phone calls 		↔			
Satisfaction survey 					X

 Participation will commence once eligibility is confirmed via urine analysis (or culture for those individuals with a positive UA); an order for study product will be faxed/mailed to the Research Pharmacy; intervention start date will be the first dose listed on the dosing diary. If the dosing diary is not available, the intervention start date will be recorded as the date told to the study team by the participant and documented in the REDCap database.

 A rapid UA will be performed as part of standard of care at the time of screening; UAs at Visit 2 will be study-paid; positive tests will be followed with a urine culture; test results usually take about 4 days

 QOL measures include the following standardized surveys: Neurogenic Bladder Symptom Score; Neurogenic Bowel Dysfunction Score; SF-Qualiveen; SCI-QOL Measurement System's *Bladder Management Difficulties*, *Bladder Complications*, *Bowel Management Difficulties*, and *Satisfaction with Social Roles and Activities*; and Community Participation Indicators Scale (see Section 8.1, "Efficacy Assessments")

 Study team will make phone calls every two weeks +/- 3 business days to participants throughout the study period to ask about UTIs, adverse events, compliance and general health updates.

 Study team will conduct this visit, likely over the phone, within 30 days after the participant's final instillation in order to assess any adverse events or reactions while the study drug is washing out of the participant's system

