## 4 STUDY DESIGN

### 4.1 OVERALL DESIGN

#### KEY DESIGN DETAILS

- Hypothesis - The use of intravesical gentamicin will reduce the incidence of UTIs, bladder complications, bowel complications, and will enhance subject's quality of life.
- Pre-post study design, comparing participants number of UTIs during the six-month treatment period to the number they incurred during the six months prior to treatment.
- Participants will begin with active treatment, using gentamicin + saline solution, after they have completed the baseline interview and required urinalysis and bloodwork.
- Phase 2/3
- Single-site - Michigan Medicine in Ann Arbor, MI.
- Dosing – Instillations of treatment solution will occur nightly after the subject's last evening catheterization.
- Interim analysis – The study design and intended sample size preclude meaningful interim analyses.

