## 4.2 SCIENTIFIC RATIONALE FOR STUDY DESIGN

This study's pre-post design is selected because it provides substantially more statistical power than a parallel group design with a similar sample size and allows participants to serve as their own controls, without requiring them to use placebo for half of the study. Our prior project experience, using a cross-over design indicated that subjects are likely to drop out if they think that they are receiving placebo.

- Treatment (gentamicin plus saline) is administered to each study participant for six months.
- This design provides the benefit of a direct comparison within participants (the effect of no treatment vs. treatment).
- Superiority trial – this design allows one to determine a clinically relevant difference between no intervention and the study intervention.

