### 5.4 SCREEN FAILURES

Screen failures are defined as those individuals who consented to participate in the study, but who are subsequently deemed ineligible, usually after the screening visit urine analysis and culture.

Individuals who test positive for a UTI at their screening visit may be re-assessed for eligibility after prescribed antibiotic use. Individuals who undergo a second positive urine tests with UTI symptoms following treatment are ineligible for the study (i.e.; categorized as a screen failure).

Additionally, females of childbearing potential who have a positive screening pregnancy test will be categorized as a screen failure.

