## 6.2 PREPARATION/HANDLING/STORAGE/ACCOUNTABILITY

### 6.2.1 ACQUISITION AND ACCOUNTABILITY

Michigan Medicine Research Pharmacy will maintain study medication supply (both active and control products) and be responsible for dispensing the medication and study supplies (syringes, needles, catheter tips, and dosing logs) directly to the participant. Participants will receive their study medication in the mail via ground delivery. A signature at delivery is preferred. The Research Pharmacy will maintain shipping records and the study team will follow-up with participants to ensure receipt of study materials at the appropriate bi-weekly visit. The study participants will be asked to maintain a dosing log and review educational materials supplied by the study team. They are not required to save the used syringes but should refrain from re-using the syringes.

The Research Pharmacy and Study Team shall retain records of the following:

- Product shipped date.
- Product received date.
- Quantity of product shipped.
- Batch/serial numbers of products.
- Product expiration dates.
- Participant compliance.

The study team will call participants to confirm receipt of study product. Accommodations will be made for vacations and other travel away from home.

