## 9 STATISTICAL CONSIDERATIONS

### 9.1 STATISTICAL HYPOTHESES

Our primary hypothesis (H1) is that during the six-month treatment period, incidence of UTIs will be significantly lower than it had been during the six months prior to the treatment period. Our Secondary Hypothesis (H2) states that there will be significantly fewer bladder and bowel complications as reported on the various patient-reported outcome measures at the end of treatment than there had been on the baseline interview, just prior to the start of treatment.

Our tertiary hypotheses (H3 and H4) center on health-related quality of life and community participation. We expect that at the end of the treatment period, QOL will be significantly higher than it had been at the time of the baseline interview, prior to treatment (H3). Similarly, we expect that at the end of the treatment period, community participation will be significantly better than it had been at the time of the baseline interview (H4).

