### 9.2 SAMPLE SIZE DETERMINATION

Power calculations were conducted based on the **primary hypothesis that incidence of UTIs will be significantly lower during the treatment period (gentamicin + saline) than during the prior six months.**

In calculating power, we assume that during the study period, there will be a 50% reduction in UTIs from the number that participant experienced during the prior six months, which serves as the control period. These assumptions are based on the findings of a six-month retrospective study of gentamicin. Calculations of power were conducted assuming that paired samples t-tests will be used to assess the first hypothesis. While we may consider using other additional ways of determining differences in UTIs between the baseline and trial periods, paired samples t-tests will be used at least initially. Because we are working with count rather than continuous data, the t-tests will be conducted using natural log-transformed infection rates rather than the raw rates. Based on our assumptions, the sample size needed to have a power of at least 80% will be 15. This is the necessary sample size of participants who complete the study. SPSS version 28 was used to conduct this power analysis.

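### Entry requires at least 2 UTIs in a window that largely overlaps the untreated comparator, so the pre-post change includes regression to the mean and is not an estimate of the gentamicin effect alone

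*Protocol*

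**What the plan says.** **Selection.** Protocol section 5.1 requires a "History of at least 2 UTIs documented in the EMR during the previous six months (prior to screening").

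**Comparator.** Section 4.1 describes a "Pre-post study design, comparing participants number of UTIs during the six-month treatment period to the number they incurred during the six months" before treatment. Section 9.1 hypothesises that "incidence of UTIs will be significantly lower than it had been during the six months prior to the treatment period". Section 9.2 assumes a 50% reduction "from the number that participant experienced during the prior six months, which serves as the control period". There is no concurrent control (sections 4.1 and 4.2). Section 10.1.9.1 names the medical record as the source for counting UTIs, so eligibility and outcome counts share a source.

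**Timing.** Screening runs from Day -30 to 0 (section 1.3), and the "intervention start date will be the first dose listed on the dosing diary". Section 6.2.1 adds that "Participants will receive their study medication in the mail via ground delivery". Section 5.4 adds that "Individuals who test positive for a UTI at their screening visit may be re-assessed for eligibility after prescribed antibiotic use".

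**Analysis.** Section 9.4.2 plans a paired t-test on log-transformed rates and possibly a Poisson mixed model. The SAP instead takes incidence rate ratios of each later period (treatment, one month post, six months post) against pre-treatment. Neither document mentions regression to the mean.

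**Claim.** Section 4.2 says "this design allows one to determine a clinically relevant difference between no intervention and the study intervention".

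**The concern.** A person's six-month UTI count is partly their own rate and partly chance. Requiring at least 2 events admits people whose count was high by chance as well as people whose rate is high. Reusing most of that window as the comparator puts the favourable chance into the pre-treatment side only, because the treatment-period count is not selected. The expected change is then a fall even if the drug does nothing.

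At stake is how Hypothesis 1 is read. A significant fall could be reported as the gentamicin effect. The SAP's post-treatment ratios use the same pre-treatment reference, so a rate that stays below it after treatment could likewise be read as lasting benefit.

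**Working it through.** **The plan's own figure.** Section 9.2 gives 15 completers for at least 80% power at a 50% reduction. Paired t power uses the noncentral t with n - 1 degrees of freedom and noncentrality √n × ln 2 / SD. At two-sided 5% and n = 15, 80% power needs ln 2 / SD = 0.778, so SD = 0.693 / 0.778 = 0.89. At n = 14 it needs 0.810, so SD = 0.86. Fifteen is therefore attainable for an SD of about 0.86 to 0.89, but the SD is not stated, so the figure cannot be verified. The calculation contains no allowance for selection.

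**Inputs from the documents.** Threshold of 2; 180-day periods; n = 15; 5% level (two-sided assumed, so 2.5% in the reduction direction).

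**Assumed.** Poisson counts with stable individual rates, either common to all or gamma-distributed with shape 4, 2 or 1; mean m = 1.5 to 5 UTIs per 180 days before the entry rule; no drug effect; equal detection; 150 or 120 of the 180 comparator days shared with the eligibility window. A 30-day interval from screening to first dose gives 150. Also assumed: 0.5 added to counts before taking logs, and an exact conditional test of the pooled ratio. The documents specify neither.

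**Step 1, full overlap.** Apparent reduction R = 2P(Y=2) / (m - P(Y=1)).
- Common rate, m = 1.5: P(Y=1) = 0.3347, P(Y=2) = 0.2510, so R = 0.502 / 1.165 = 0.431.
- Shape 1, m = 3: P(Y=1) = 0.1875, P(Y=2) = 0.1406, so R = 0.281 / 2.813 = 0.100.

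**Step 2, partial overlap.** With shared fraction s, reduction = sR / (1 - (1 - s)R).
- R = 0.431: 0.387 at s = 150/180; 0.335 at s = 120/180.
- R = 0.100: 0.085 and 0.069.

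**Step 3, UTI-free days before screening.** Suppose the 14 days before screening must be UTI-free. The 2 events must then fall in 166 days, and only 150 - 14 = 136 shared days can contain any. For a common rate of 1.5:
- Mean over 166 days: 1.5 × 166/180 = 1.383.
- Mean given at least 2 events: (1.383 - 0.347) / (1 - 0.251 - 0.347) = 2.58.
- Comparator: 2.58 × 136/166 + 1.5 × 30/180 = 2.36.
- Reduction: 1 - 1.5/2.36 = 0.36.

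The same steps for a common rate of 5 give a comparator of 4.84 × 136/166 + 5 × 30/180 = 4.79, against 5 on treatment: an apparent increase of about 4%.

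**Step 4, simulated trials of 15, means 1.5 to 3.**

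| Shared days | UTI-free days | Apparent reduction | Significant: log paired t | Significant: exact pooled ratio |
|---|---|---|---|---|
| 150 | 0 | 8–39% | 13–67% | 6–40% |
| 120 | 0 | 7–34% | 9–42% | 5–27% |
| 150 | 14 | 5–36% | 8–60% | 3–33% |
| 120 | 14 | 2–30% | 5–33% | 3–19% |

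The top of each range needs a mean of 1.5 and no between-person variation. At means 4 to 5 without UTI-free days the reduction is 2.3–6.8%; with 14 such days the net bias is about zero or slightly reversed. The mixed model was not simulated, but as described it has no term for the selection.

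**Step 5, detection.** Without UTI-free days, treatment-period detection of 1/(1 - 0.069) = 1.07 to 1/(1 - 0.387) = 1.63 times the pre-treatment level would cancel the bias.

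**The case against.** The pre-post design was chosen deliberately, with reasons given in section 4.2, and two features oppose the bias. Section 5.2 excludes a current UTI at screening, and section 5.4 allows re-assessment only after treatment, so days inside the comparator are forced to be UTI-free. Contact every two weeks with record review (section 8.1) and prompts to seek care (section 2.3.1) probably raise detection on treatment. If UTIs are frequent in this population, little net bias remains.

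All of this stands. It limits the size, but neither feature was designed as a correction, neither is quantified, and the documents give no rate that places the trial in the range where the bias is small.

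The overlap is also not fixed. Sections 4.1 and 9.1 end the comparator at treatment, section 4.4 at the start of study participation and section 10.1.6 at enrolment. Depending on which applies, the shared days could be anywhere up to nearly all 180.

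A reader might go further and infer that a significant result would be an artefact, that the net bias must favour gentamicin, or that the planned analysis is invalid. The documents support none of these. Among the settings above, a false significant result is more likely than not only for the log paired t at a mean of 1.5, 150 shared days and little or no between-person variation. Hypothesis 1 in section 9.1, as a statement about change, can stand.

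**Conclusion.** The mechanism is certain: selection on a count that is largely reused as the comparator pushes the pre-post comparison toward a reduction, and no planned analysis corrects for it. The statement in section 4.2 that the design determines the difference from no intervention is therefore not supported. A significant fall cannot be read as the gentamicin effect alone, and a post-treatment rate below pre-treatment cannot be read as lasting benefit.

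The size is illustrative only. It rests on an unknown UTI rate, unknown between-person spread, stable rates, the assumed shared and UTI-free days, and equal detection; closer detection on treatment would lower it further. Confidence is high for the mechanism and not for the size. This is a cheap improvement to analysis and interpretation, not a reason to change the eligibility rule or abandon the planned comparison.

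**What to change.** 1. **Wording.** Revise section 4.2 and the SAP's reporting of Hypothesis 1, for example: *The pre-post difference is a change from a baseline selected for at least 2 UTIs. It includes regression to the mean and is not an estimate of the gentamicin effect alone.* Apply the same caveat to the post-treatment ratios against pre-treatment.

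2. **One added contrast.** Report the treatment versus six-month post-treatment rate ratio with its confidence interval, from periods the SAP already has. Use the same UTI definition (section 4.1) and record source (section 10.1.9.1), with and without known post-study gentamicin users (section 8.2). Rates that stay low off drug would suggest regression to the mean; a rebound would suggest a drug effect. State the limits. Visit 3 may fall from day 60 after treatment, so later use may be unknown. Detection may also be lower: section 8.3.4 ties two-weekly contact to the intervention, although sections 1.3 and 8.1 can be read more broadly. For a true 50% reduction at means 1.5 to 3, power is 41–74% (paired t) or 42–90% (exact) if rates return fully. It is 22–40% or 23–64% if an assumed 30% continue gentamicin. A missing rebound is not proof of regression to the mean.

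3. **Supportive check only.** Compare treatment-period UTIs with record days -360 to -181 before screening, where available. People can enter six months after initial discharge (section 5.1), so some lack that window. The check relies on stable rates and can mislead either way. If the earlier rate was 1.2 to 1.5 times the later one, false positives are 9–50% (paired t) or 7–71% (exact). If it was lower, a true effect is understated.

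4. **Definition.** State one end date for the pre-treatment window.

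The SAP is written in the past tense. If treatment-period data have already been analysed, label items 2 and 3 post hoc.

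**Cost.** Wording changes, one ratio from periods already planned, and about 180 more days of record abstraction for about 15 people.

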### 5.2 EXCLUSION CRITERIA

The EMR will be pre-screened for contraindications to participation based on medical history. Criteria will be confirmed by patient or caregiver report at the screening assessment. Final eligibility will be ascertained at the baseline assessment following confirmation of criteria by patient or caregiver report and a urine analysis.

- Concurrent use of *systemic* oral or intravesical antibiotic prophylaxis during the previous six months.
  - Localized antibiotic therapies (i.e. topical antibiotic creams) are permitted
- EMR-documented or self-reported history of gentamicin allergy.
- Patients who are 80 years old or older.
- Positive pregnancy test at screening (for female patients who are of childbearing age).
  - Subjects who are not pregnant and who are willing and able to use appropriate contraception while enrolled in the study intervention will be permitted.
- Patients with a history of 8th cranial nerve disorder.
- Co-morbidities like cancer and chronic disease that could impact patient safety OR significantly affect the rate of UTIs and/or QOL substantially.
- Urological co-morbidities like bladder cancer and history of kidney disease. Co-PI [name] will review all cases where there is any question about possible inclusion of persons with a history of kidney disease. These include:
  - Patients with EMR-documented renal impairment (e.g. end-stage renal disease, documented glomerular filtration rate (GFR) less than 60 ml/min will be excluded (most recent result)).
  - Patients with active pyelonephritis (patients with a history of pyelonephritis, which has been treated and is resolved, will be permitted in the study.)
- Current UTI at screening visit, assessed via urine analysis, culture, and symptoms.
- Concurrent enrollment in a similar clinical trial
- Concurrent use of contraindicated diuretics (ethacrynic acid, furosemide)
- Current use of other contraindicated or disallowed concomitant medications or receiving treatments that may influence the results from this study.
- Known allergy to aminoglycoside antibiotics.
- Otological symptoms at baseline (i.e., tinnitus, severe dizziness/vertigo).
- At the discretion of study team, individuals who are unable or unlikely to comply with procedures and/or for whom study participation is not recommended (e.g. unable to arrange transportation and/or reliable assistance to perform instillations, cognitive and/or behavioral challenges that preclude meaningful participation, poor health, etc.)

### 5.3 LIFESTYLE CONSIDERATIONS

Participants should show indications of health seeking behaviors (i.e. following bladder management procedures), and be able to consult with their personal physicians when noticing symptoms related to bladder complications and/or UTIs. They should have access to caregivers or family members, as needed, to assist them with instillations following regular catheterizations. Healthy behaviors related to hygiene when having to catheterize and during bowel management procedures are also important.

During this study, the management of all ongoing and new bladder or bowel issues will continue to fall under the purview of the participant's treating physician or care provider. The study team will not offer treatment for any new-onset UTIs, in their role on the study. This means that participants are expected to contact their provider about any new symptoms or infections. Since the physicians on the study team also provide treatment to SCI/D patients for urinary issues, in this clinician role, they may provide participants with care.

Participants or their assistants should be willing to follow study protocol for storage of the medication and preparation of dose for daily instillations as well as complete their dosing diaries.

Dietary restrictions and activity limitations are not required for participants while they are enrolled in this study. Should a participant start one of the contraindicated diuretics above, or become pregnant, they will discontinue the study treatment and notify the study team. Female participants will be asked about pregnancy and compliance with the use of contraception during their bi-weekly follow up visits.

